5.1. Analysis Specifications

5.2. Level of Significance

All statistical testing will be performed using a 2-sided test at the 10% level of significance, unless otherwise noted. Confidence intervals will be presented as 2-sided 90% confidence intervals.

Testing of Secondary Endpoints

The secondary endpoints are to be tested sequentially at the nominal 0.10 significance level (2-sided). The order of these endpoints is as follows:

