5.5.3. Overall Response Rate

Overall response rate is defined as the proportion of subjects achieving a best overall response of either CR (including CR_b and CR_u) or PR as evaluated by IRC.

All randomized subjects with a measurable disease at baseline will be included in this analysis. Subjects with missing post-randomization data are considered non-responders.

Overall response rate will be estimated according to the crude proportion of confirmed responders (PR or better) based on the best overall response and summarized by treatment arm. Overall response rate will be compared between treatment arms using a 2-sided chi-square test at the 10% level of significance and 90% confidence intervals.

The relative risk (ibrutinib + CIT vs. CIT) will be reported along with the associated 95% confidence interval. Statistical inference will be evaluated using Chi-square statistic.

For overall response rate based on investigators' assessment, same analysis methods used for IRC reported overall response will be used.

Subgroup analysis for ORR may be performed if the number of responders within each subgroup is sufficient.

For enrolled subjects in Part 1, IRC and investigator response will be listed.

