5.5.4. Tumor Volume Reduction Rate

The tumor volume reduction rate will be measured as the mean change in the sum of the products of the lesion diameters (SPD) from baseline to Day 14. The means will be compared between treatment arms using a 2-sided t-test at the 10% level of significance. The mean difference and its associated 90% confidence interval will be provided.

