5.5.6. Subjects Who Proceed to Stem Cell Transplantation

The rate of subjects who proceed to stem cell transplantation will be estimated according to a proportion summarized by treatment arm. The rate will be compared between treatment arms using a 2-sided chi-square test at the 10% level of significance and 90% confidence intervals. Logistic regression analysis will also be performed to estimate an odds ratio and the associated 90% CI between the 2 treatment groups.

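### SAP 5.5.3 gives the ORR relative risk a 95% interval, while the ORR test is at 2-sided 10% and every other efficacy interval with a stated level in the SAP is 90%

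*SAP*

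**What the plan says.** SAP 5.2 (Level of Significance) gives the general rule for tests: "All statistical testing will be performed using a 2-sided test at the 10% level of significance, unless otherwise noted". Its rule for intervals carries no qualifier: "Confidence intervals will be presented as 2-sided 90% confidence intervals". Protocol Section 11 sets the same two levels.

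SAP 5.5.3 (Overall Response Rate) follows this for the comparison of arms, "using a 2-sided chi-square test at the 10% level of significance and 90% confidence intervals". Its next paragraph turns to the relative risk of ibrutinib plus CIT against CIT, which "will be reported along with the associated 95% confidence interval". The sentence after that reads "Statistical inference will be evaluated using Chi-square statistic". No reason is given for the different level, and SAP Section 9 (Changes to Protocol Specified Analyses) has no text.

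The nearest parallels use 90%:
- SAP 5.5.6, a chi-square comparison of transplant rates: "Logistic regression analysis will also be performed to estimate an odds ratio and the associated 90% CI between the 2 treatment groups".
- SAP 5.5.4, tumor volume: "The mean difference and its associated 90% confidence interval will be provided".
- EFS (5.4.2), the EFS subgroups (5.4.5), overall survival (5.5.1) and duration of response (5.5.5) also have 90% intervals.

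**The concern.** A 95% interval is the counterpart of a 2-sided 5% test, but ORR is tested at 10%. For results with p between 0.05 and 0.10, the plan would call ORR significant and print beside it an interval that includes no effect. ORR is first in the secondary testing order in SAP 5.2, so readers will look closely at this result. The same methods apply to investigator-assessed ORR, so the mismatch would appear twice. What is at stake is a clear report and a relative risk whose precision can be read on the same scale as the hazard ratios and the other effect estimates.

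**Working it through.** The plan states no power or sample size for ORR, so there is no ORR figure to reproduce. The check asks how often test and interval would disagree.

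**Inputs.** About 72 subjects randomized 2:1, hence 48 vs 24 (SAP 1.4). The test is 2-sided at 10% (SAP 5.2 and 5.5.3). Two assumptions are added: all subjects have measurable disease, and the interval is a Wald interval on the log relative risk. The SAP names no interval method.

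**Formulas**, with *a* of 48 responders on ibrutinib plus CIT and *b* of 24 on CIT:
- Test: z = (a/48 − b/24) / √[p̄(1 − p̄)(1/48 + 1/24)], with p̄ = (a + b)/72; chi-square = z².
- Interval: exp[ln RR ± q·SE], with SE = √(1/a − 1/48 + 1/b − 1/24); q = 1.645 for 90% and 1.960 for 95%.

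**Example: 35/48 (72.9%) vs 12/24 (50.0%).**
- p̄ = 47/72 = 0.653; z = 0.2292/0.1190 = 1.925; p = 0.054, significant at 10%.
- RR = 1.458; ln RR = 0.3773; SE = 0.2223.
- 90%: exp(0.3773 ± 0.3656) = 1.01 to 2.10, excludes 1.
- 95%: exp(0.3773 ± 0.4356) = 0.94 to 2.25, includes 1.

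**All tables.** Of the 48 vs 24 tables that favour ibrutinib with p < 0.10 and have at least one control responder (so that the relative risk is defined), there are 384.

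| Wald interval | Includes 1 |
|---|---|
| 95% | 74 |
| 90% | 25 |

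The change of level therefore resolves 74 − 25 = 49 tables.

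**What the 74 consist of.** In 40 of them p < 0.05, so a 95% interval would be expected to exclude 1 if it inverted the test. They conflict because the Wald interval does not. For example, 39/48 vs 14/24 gives p = 0.038 but a Wald 95% interval of 0.967 to 2.005. The other 74 − 40 = 34 have p between 0.05 and 0.10; there the level alone produces the conflict, even for an interval that inverts the test exactly.

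**What remains at 90%.** 34/48 vs 12/24 gives z = 0.2083/0.1201 = 1.735 and p = 0.083, yet the Wald 90% interval is 0.980 to 2.048. A score interval avoids this. At RR = 1 its statistic equals the pooled z, and 1.735 exceeds 1.645, so the 90% score interval excludes 1.

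**As a probability.** A table count is not a probability. Assume a control ORR of 60% (the RICE figure in Protocol 1.2, used only for illustration) and the Wald interval. The share of significant results favouring ibrutinib whose interval includes 1 is then:

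| Assumed ibrutinib ORR | 95% interval | 90% interval |
|---|---|---|
| 70% | 65% | 27% |
| 80% | 46% | 18% |
| 85% | 34% | 11% |

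**The case against.** The strongest reply is that nothing turns on this interval. SAP 5.5.3 bases inference on the chi-square statistic, so ORR success, the type I error rate and the order of secondary tests are the same whatever interval is printed. That stands. A reader might infer from ORR's place at the head of the sequence that the 95% interval could block or open the later tests; the SAP does not support that.

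Second, SAP 5.3.1 and Protocol 11.3 allow departures from 90% where another level is stated, so 5.5.3 could be a permitted exception. On the wording of 5.3.1 this is fair. The interval sentences in SAP 5.2 and Protocol Section 11 have no such allowance, however, and a deliberate 95% interval would still not match the 10% test in its own section.

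Third, much of the disagreement comes from the Wald method, which the SAP does not specify. This also stands, and it is why all 74 tables cannot be put down to the level.

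Fourth, formal ORR testing requires rejection of the primary hypothesis (SAP 5.2). Protocol 11.9.1 reports that the futility boundary was reached at 31 of 60 EFS events and that enrollment stopped. A formal ORR success is therefore unlikely, and 48 vs 24 describes the planned trial, not necessarily the final one. The relative risk nevertheless remains a planned output.

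A 95% interval also appears in Protocol 11.4, but as a pharmacokinetic precision target. It has a different purpose and is not an efficacy interval.

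**Conclusion.** The interval level for the ORR relative risk in SAP 5.5.3 is inconsistent with the ORR test, with the general rule in SAP 5.2 and with the other SAP efficacy intervals that state a level. It is a minor point of reporting and interpretation.

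At the planned 48 vs 24, with all subjects measurable and a Wald interval, the 95% interval includes 1 in 74 of 384 significant tables favouring ibrutinib, against 25 at 90%. It would be tempting to conclude that changing the level removes the conflict entirely. It does not with a Wald interval, since 25 tables remain. The counts depend on the assumed arm sizes and interval method; the mismatch of level does not.

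**What to change.** In SAP 5.5.3, change 95% to 90% for the relative risk, and preferably name a score-based 90% interval so that it agrees with the uncorrected chi-square test. Apply the same to investigator-assessed ORR, which uses the same methods. If 95% was intended, state the reason and note that the interval does not correspond to the 10% test.

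The cost is one number and, ideally, the name of a method. No test, alpha, sample size or data collection changes.

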5.5.4. Tumor Volume Reduction Rate

The tumor volume reduction rate will be measured as the mean change in the sum of the products of the lesion diameters (SPD) from baseline to Day 14. The means will be compared between treatment arms using a 2-sided t-test at the 10% level of significance. The mean difference and its associated 90% confidence interval will be provided.

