
 Evaluate the safety and tolerability of ibrutinib in combination with RICE or RVICI background therapy in pediatric subjects and young adults with B-cell malignancies Determine the ORR Evaluate tumor volume reduction at Day 14 Determine the number and proportion of subjects who proceed to stem cell transplantation Evaluate the time to response Measure the duration of response Evaluate long-term survival (EFS at 2 and 3 years) Evaluate overall survival Assess disease-specific biomarkers Assess the pharmacodynamic response, if deemed appropriate based on Part 1 results Assess the population pharmacokinetics of ibrutinib in pediatric subjects and young adults Acceptability and palatability assessment of all ibrutinib formulations 	
 Safety parameters, including gastrointestinal effects, immune function, intensified cardiac monitoring (in particular, after previous anthracycline exposure) The proportion of subjects who achieve CR, (including CR_b and CR_u) and PR Percent decrease in the sum of the products of the lesion diameters at Day 14 Number and proportion of subjects who proceed to stem cell transplantation The time interval from the first dose of ibrutinib to the first documented response for those subjects who respond Duration calculated from the date of initial documentation of a response (CR or PR) to the date of first documented evidence of PD or death Proportion of subjects with EFS at 2 and 3 years The duration from the date of randomization to the date of the subject's death Phosphor-BTK, as well as SYK, STAT3, caspase-3, BCL-xL, and cIAP1 expression at baseline and during treatment BCR/CD79B, CARD11, and MYD mutations c-MYC, immunoglobulin, and T-cell receptor gene rearrangements at baseline BTK occupancy Population pharmacokinetic parameters and derived systemic exposure to ibrutinib such as AUC Relationship between pharmacokinetic parameters and age or measure of body size Visual analog scale score for palatability
Exploratory	

 Evaluate other response biomarkers Explore the exposure-response relationships 	
 Other biomarkers, as applicable Potential relationships between systemic exposure and response

Refer to Section 9, Study Evaluations, for evaluations related to endpoints.

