11.3. Efficacy Analyses

Descriptive statistics and subject listings will be used to summarize the data. For continuous variables, the number of observations, means, standard deviations, medians, and ranges will be used. For discrete variables, frequency will be provided. For time-to-event variables, Kaplan-Meier estimates will be provided.

Comparisons between the 2 treatment arms in Part 2 will be performed as follows: for the continuous variables representing change from baseline to a particular postbaseline timepoint, analysis of variance will be used. For discrete variables, Chi-square test will be used. For time-to-event variables, non-stratified log-rank test and non-stratified Cox proportion hazard model will be used unless specified otherwise. All tests will be conducted at 2-sided test at the 10% level of significance and 90% confidence intervals will be provided, unless otherwise stated.

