11.3.2. Secondary Endpoints

Secondary endpoints in Part 1 (Section 2.1.1) will be provided as listings. In Part 2, tumor volume reduction at Day 14, ORR, time to response, duration of response, overall survival, and number (%) of subjects who proceed to stem cell transplantation will be summarized. Other secondary endpoints will be provided as listings.

Overall survival is defined as the duration from the date of enrollment (in Part 1) or randomization (in Part 2) to the date of the subject's death. Overall survival will be analyzed using the non-stratified log-rank test for treatment comparison in Part 2. The overall survival distribution and median overall survival with its 90% confidence interval will be estimated using the Kaplan-Meier product-limit method. The hazard ratio for ibrutinib+CIT relative to CIT alone and its associated 90% confidence interval will be calculated based on the non-stratified Cox proportional hazards model. Exploratory analysis using the Cox proportional hazards model with and without the covariates, as well as exploratory analysis on the effect of subsequent antilymphoma therapy on overall survival, will be performed as appropriate.

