11.9.1. Outcome of IDMC review on 20 July 2020

The pre-planned interim analysis was conducted per the specifications outlined in Section 11.9 to determine the appropriateness for early stopping using the nonbinding stopping rules, in addition to a review of the efficacy and safety of patients in Part 2 of this study. As the futility boundary for early stopping was reached (31 of 60 EFS events), the IDMC recommended stopping enrollment. Consequently, new patient enrollment has ceased. No new safety concerns were identified. Follow-up of the ongoing patients will continue per guidance in Section 9.1.3 and Section 9.1.4, until the sponsor decides to stop the study.

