5. EFFICACY

Analysis of efficacy endpoints will be conducted on the ITT population. [Table 3](#) summarizes the efficacy endpoints and analysis methods to be performed.

Table 3: Summary of Efficacy Analyses to be Performed

Endpoint	Analysis	Analysis Method	Population
Primary			
Event-free Survival (EFS) as assessed by IRC	Primary	Non-stratified log-rank test, non-stratified Cox regression model, all PD and death considered as events regardless of subsequent antilymphoma therapy or a conditioning regimen for stem cell transplantation. EFS is defined as the time interval from randomization to death, disease progression, or lack of CR or PR after 3 cycles of treatment.	ITT
	Sensitivity	
 1) Alternative censoring rule 1: subjects who received subsequent antilymphoma therapy or a conditioning regimen for cell transplantation are considered to have had an EFS event at the initiation of subsequent therapy 2) Alternative censoring rule 2: subjects who received subsequent antilymphoma therapy or a conditioning regimen for cell transplantation are censored at the last disease assessment showing no evidence of PD before the use of subsequent therapy 3) Alternative censoring rule 3: subjects will be censored at the last disease assessment if they progress, die or have not responded after missing ≥ 2 planned disease assessment visits. 4) Investigator assessed EFS by non-stratified log-rank test and non-stratified Cox regression model; concordance rate between the IRC-determined EFS and investigator-determined EFS 	ITT
	Subgroup	Non-stratified Cox regression model within each subgroup	ITT
Secondary			
Long-term survival (EFS) at 2 and 3 years		IRC assessed chi-square test for 2 and 3 year EFS rate.	ITT
Overall Survival	Primary	Non-stratified log-rank test, non-stratified Cox regression model, as the time interval from enrollment (Part 1) or randomization (Part 2) to all deaths considered as events regardless of subsequent antilymphoma therapy or a conditioning regimen for stem cell transplantation.	ITT
	Sensitivity	Censored at subsequent antilymphoma therapy or a conditioning regimen for stem cell transplantation.	
Overall Response in Part 1	Subgroup	Non-stratified Cox regression model within each subgroup Listing of IRC and investigator assessments for those subjects who respond.	ITT Enrolled subjects

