Overall Response Rate in Part 2	Primary	IRC assessed ORR chi-square test, Logistic regression model	ITT subjects with measurable disease at baseline
	Sensitivity	Investigator assessed ORR chi-square test, Logistic regression model	
	Subgroup	Logistic regression model	
Tumor Volume Reduction Rate		Analysis of variance (t-test) for percent decrease in the sum of the products of the lesion diameters at Day 14	ITT subjects with measurable disease at baseline
Time to Response		Non-stratified log-rank test, as the time interval from randomization to response for those subjects who respond as	ITT subjects who responded

Table 3: Summary of Efficacy Analyses to be Performed

Endpoint	Analysis	Analysis Method	Population
		assessed by IRC.	
Duration of Response		Non-stratified log-rank test, as the time interval from date of initial documentation of a response to the date of first documented evidence of progressive disease (PD) or death as assessed by IRC.	ITT subjects who responded
Rate of Subjects Who Proceed to Stem Cell Transplantation		Chi-square test for percent of subjects who proceed to stem cell transportation, Logistic regression model.	ITT
Other			
Subsequent Therapy		Descriptive summary Non-stratified log-rank test for the effect of subsequent antilymphoma therapy or a conditioning regimen for stem cell transplantation on overall survival, will be performed, as appropriate.	ITT subjects
Risk factors		Non-stratified Cox proportional hazards model using covariates to analyze the effect on EFS and survival will be performed, as appropriate.	ITT

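### SAP 5.5.4 words Day-14 tumour volume reduction as a mean change in SPD, whereas SAP Table 3 and the protocol make it a percent decrease

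*SAP*

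**What the plan says.** Four places state the endpoint.

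- Protocol Synopsis and Protocol 2.1.2, Part 2 secondary endpoints: "Percent decrease in the sum of the products of the lesion diameters at Day 14".
- SAP Table 3, method column: "Analysis of variance (t-test) for percent decrease in the sum of the products of the lesion diameters at Day 14". Its population column reads "ITT subjects with measurable disease at baseline". SAP section 5 introduces the table as one that "summarizes the efficacy endpoints and analysis methods to be performed".
- SAP 5.5.4: the quantity is "measured as the mean change in the sum of the products of the lesion diameters (SPD) from baseline to Day 14". The arm means are then compared by a two-sided t-test at 10%, and the mean difference is reported with a 90% confidence interval. The section does not say percent and does not divide by baseline.

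Four other passages bear on the point. Protocol 11.3 has a general rule, repeated in SAP 5.3.1: "for the continuous variables representing change from baseline to a particular postbaseline timepoint, analysis of variance will be used". Protocol 11.3.2 lists the Part 2 secondary endpoints to be summarised, and the list opens "In Part 2, tumor volume reduction at Day 14, ORR, time to response, duration of response, overall survival". SAP 5.2 puts this endpoint fifth of six in a sequence that starts only if the primary hypothesis is rejected. SAP section 9, reserved for changes to protocol-specified analyses, has a heading and no entries.

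**The concern.** SAP 5.5.4 is the section devoted to this endpoint, and the only place that names its estimate and interval. A programmer following it literally would take Day-14 SPD minus baseline SPD, in area units, with shrinkage negative. A programmer following Table 3 would take a percentage of baseline, with shrinkage positive. Both could say that they followed the SAP.

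At stake are the unit and sign of the reported mean difference and, potentially, which arm looks better. On the absolute scale, subjects with a large baseline SPD carry most of the weight, and a chance difference in baseline tumour burden between arms can look like a treatment difference. The percent scale gives each subject equal weight, and it is the scale that the protocol chose.

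**Working it through.** The documents give no effect size, SD, power or SPD distribution for this endpoint, so there is no planned figure to reproduce. The check is a comparison of texts followed by simple arithmetic.

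**1. The definitions side by side**

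| Place | Quantity | Relative to baseline? |
|---|---|---|
| Protocol Synopsis | percent decrease in SPD | yes |
| Protocol 2.1.2 | percent decrease in SPD | yes |
| SAP Table 3 | percent decrease in SPD | yes |
| SAP 5.5.4 | mean change in SPD | not stated |

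With two arms, a one-way analysis of variance and the usual t-test are the same test. Table 3 and 5.5.4 therefore describe one analysis with two response variables. The general rule in Protocol 11.3 and SAP 5.3.1 does not settle which, because change from baseline fits either scale.

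**2. How the scales relate**

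Let B be baseline SPD and D be Day-14 SPD, with shrinkage positive.

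- Absolute decrease: a = B − D.
- Percent decrease: p = 100 × (B − D) / B.
- Hence a = B × p / 100. An arm mean of a weights each subject's percent decrease by baseline SPD; an arm mean of p does not. Subjects, and so arms, can be ordered differently on the two scales.

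**3. An example of reversal**

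Inputs: Protocol 4.1 admits a lesion just over 1 cm in each diameter, so about 1 cm². Protocol 9.2.5.1 allows up to six masses to be measured. The 3 × 3 cm size used below is an assumption for illustration, giving 6 × 3 × 3 = 54 cm².

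- Subject 1: B = 1, D = 0. p = 100 × 1 / 1 = 100%; a = 1 cm².
- Subject 2: B = 54, D = 48.6. p = 100 × 5.4 / 54 = 10%; a = 5.4 cm².

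Subject 1 does better on the percent scale and subject 2 on the absolute scale.

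**4. Where the order reverses**

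An x% shrinkage of baseline B exceeds 1 cm² when B × x / 100 > 1, that is, when B > 100 / x:

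- x = 10: B > 10 cm²
- x = 25: B > 4 cm²
- x = 50: B > 2 cm²

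Extreme tumour burden is not needed for the two scales to disagree.

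**5. Who has a value**

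The percent decrease needs B > 0 and a Day-14 measurement. Under Protocol 9.2.2 and 9.2.5, subjects with marrow-only disease and no nodal disease at screening need no later imaging. Without measured lesions they have no SPD change on either scale.

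**The case against.** The strongest reply is that 5.5.4 is terse rather than contradictory. It never says absolute, a percent change is also a change from baseline, and its heading calls the measure a rate. Table 3 is in the same SAP, ties percent decrease to the same t-test, and agrees with both protocol statements. This makes percent decrease the probable intention. It does not remove the conflict, because 5.5.4 sets the estimate and interval and, as worded, defines a different quantity.

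A second reply is that little depends on it. That largely stands. Protocol 11.9.1 records: "As the futility boundary for early stopping was reached (31 of 60 EFS events), the IDMC recommended stopping enrollment". With the sequential rule in SAP 5.2, a formal test of the fifth secondary endpoint is unlikely. Protocol 9.1.3 and 9.2.5 also call the Day-14 imaging exploratory; that wording concerns calls of progression, but it limits the weight these scans carry.

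Three stronger readings are tempting, and the documents do not support them.

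- A reader might infer that the sponsor meant to switch to absolute change. Nothing says so. The empty section 9 is weak evidence either way: it is also silent on time to response, which Protocol 2.1.2 starts at the first ibrutinib dose and SAP 5.5.5 at randomization.
- A reader might infer a substantial loss of power. That would depend wholly on an assumed effect and an assumed spread of baseline SPD.
- A reader might infer from Table 3's population that marrow disease alone always counts as measurable. Protocol 9.2.5.1 sets a threshold of more than 25% marrow blasts in the absence of nodal disease, yet also lists marrow-limited disease as assessable. Protocol 4.1 lists measurable disease and marrow involvement as separate alternatives.

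**Conclusion.** The inconsistency is real. Followed literally, 5.5.4 gives a t-test, mean difference and interval on a quantity that is not the protocol endpoint. Confidence is high for the wording mismatch only.

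Percent decrease is the reading to keep. It is the protocol definition, and the response criteria in Protocol Table 9 also treat SPD relatively, with a 50% decrease for partial response and an increase above 25% for progression.

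The consequence is minor and confined to one late-ranked secondary endpoint. The primary event-free survival analysis and its error control are not affected. The size of any numerical difference in this trial is unknown; the arithmetic shows only that the scales are not interchangeable, and the 3 × 3 cm masses are assumed. It merits correction because a descriptive summary also needs a defined unit.

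**What to change.** In SAP 5.5.4, define the measure as the mean percent decrease in SPD from baseline to Day 14, with each subject's value equal to 100 × (baseline SPD − Day-14 SPD) / baseline SPD, so that shrinkage is positive as in Table 3 and the protocol. Keep the two-sided t-test at 10%, the mean difference and the 90% confidence interval.

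Add one sentence saying that the value is calculated only for subjects with a baseline SPD above 0 and a Day-14 SPD, and report how many in each arm qualify. This is a small clarification beyond restoring the protocol wording.

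The cost is a short edit to one SAP section. No protocol amendment, new data or section 9 entry is needed, because the protocol definition is restored. If the analysis has already been run, the report should state which scale was used.

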9.2.2. Bone Marrow/ Lymph Node Assessment

A subject may enter the study with only bone marrow disease. If this happens, then the subject will be followed by a bone marrow biopsy and/or aspirate for disease evaluations. Radiographic images are required at screening in these subjects but if no nodal disease is identified, subsequent imaging is not required. The timepoints for bone marrow evaluations are outlined in [Table 1](#), [Table 2](#), [Table 3](#), and [Table 4](#). Morphological examination and IHC or flow cytometry is required of all bone marrow specimens at screening for all subjects. If bone marrow results at screening are negative, subsequent assessments must include morphologic assessment of the bone marrow, while immunophenotyping is optional. Bone marrow procedures may be performed the day prior to the start of a treatment cycle for logistical reasons as needed.

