9.2.5.1. Evaluation of Measurable Disease

Subjects with nodal disease must have at least 1 measurable lymph node >1 cm in the longest diameter and >1 cm in the shortest diameter detected by CT scan or MRI in order to participate in this study. Measurable sites of disease are defined as lymph nodes, lymph node masses, or extranodal sites of lymphoma/leukemia. In the absence of nodal disease, the presence of blasts in the cerebrospinal fluid or $>25\%$ blasts in the bone marrow will be sufficient for measurable disease.

Up to 6 of the most representative nodal or extranodal masses should be selected for measurement in 2 perpendicular dimensions. In addition, the selection of these lesions should be from as disparate regions of the body as possible. Additional lesions that are present but not included in the assessment should be added as non-target lesions and followed throughout the study. The longest diameter of the spleen and liver will be assessed at Screening and at all subsequent disease evaluations.

All other sites of disease will be considered assessable. Assessable disease includes objective evidence of disease that is identified by radiological imaging, physical examination, or other procedures as necessary including bone marrow aspiration/biopsy or peripheral blood counts. Examples of assessable disease include bone lesions; mucosal lesions in the gastrointestinal tract; effusions; pleural, peritoneal, or bowel wall thickening; disease limited to bone marrow; and groups of lymph nodes that are not measurable but are thought to represent lymphoma.

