1.4. Sample Size Justification

Since Part 1 is to confirm that the pharmacokinetics in pediatric subjects is consistent with adults, no formal power calculations to pre-determine sample size were performed. The required number of subjects in Part 1 is based on pharmacokinetics results and clinical judgment.

In Part 2, approximately 72 subjects will be randomized. The sample size calculation for the randomized part (Part 2) is based on the assumption of 100% improvement (hazard ratio = 0.5) in median EFS in subjects receiving ibrutinib plus CIT (RICE or RVICI) compared with CIT (RICE or RVICI) (10 months versus 5 months). Utilizing a 2:1 randomization, this study will enroll approximately 72 subjects (approximately 48 subjects treated with ibrutinib [and RICE or RVICI background therapy]) during Part 2. Based on a total of 60 events for the 2 treatment groups, this study will have at least 80% power, given a 1-sided alpha of 0.05. An accrual rate of 1.44 subjects per month will result in a study duration of approximately 4.2 years.

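### Adjusting the Day-14 tumour volume comparison for baseline SPD would cost one degree of freedom and could sharpen it; the size of the gain depends on an outcome scale the SAP has not settled

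*SAP*

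**What the plan says.** SAP 5.5.4 defines the endpoint as "measured as the mean change in the sum of the products of the lesion diameters (SPD) from baseline to Day 14" and continues: "The means will be compared between treatment arms using a 2-sided t-test at the 10% level of significance". It asks for the mean difference with a 90% confidence interval.

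SAP Table 3 describes the same analysis as "Analysis of variance (t-test) for percent decrease in the sum of the products of the lesion diameters at Day 14", in the population "ITT subjects with measurable disease at baseline". The protocol's endpoint table (section 2.1.2) also defines the outcome as a percent decrease.

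The general rule in protocol 11.3, repeated in SAP 5.3.1, is that "for the continuous variables representing change from baseline to a particular postbaseline timepoint, analysis of variance will be used".

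None of these places names a baseline covariate. SAP 5.2 puts tumour volume reduction fifth of six secondary endpoints in a fixed sequence that opens only if the primary hypothesis is rejected.

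**The concern.** Among the tested efficacy endpoints, this is the one whose outcome is a continuous measurement also taken at baseline. A change in SPD cannot be formed without the baseline SPD, so the covariate costs nothing to collect.

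Tumour burden may vary widely. Entry needs only one site above 1 cm in both diameters (protocol 4.1), up to six masses are measured in two dimensions (9.2.5.1), and the bulky-disease example is a node over 10 cm (8.1.2). On the absolute scale, change is tied to starting size, because a small lesion cannot lose much area. Randomisation is stratified by histology and background therapy, and neither balances SPD directly.

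At stake is the precision of one secondary comparison and of the difference and interval to be reported from it.

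**Working it through.** **Inputs from the documents.** Two-sided alpha 0.10 (SAP 5.5.4). About 72 subjects at 2:1, hence 48 versus 24 (SAP 1.4: "Utilizing a 2:1 randomization, this study will enroll approximately 72 subjects").

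**Inputs that are assumptions.** Starting power of 80% for the unadjusted test; the correlations; equal SPD variance at baseline and Day 14 for the absolute-change figures. The documents supply none of these.

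**The plan's own power figure.** The only stated power is for EFS: at least 80% with 60 events, hazard ratio 0.5, 2:1 allocation and 1-sided 0.05. It reproduces: √(60 × 2/9) × ln 2 = 2.531; Φ(2.531 − 1.645) = 81.2%. It says nothing about the Day-14 endpoint.

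**Chance imbalance.** The standard error of the baseline difference is √(1/24 + 1/48) = 0.25 SD. An imbalance above 0.3 SD in either direction has probability 2 × [1 − Φ(0.3/0.25)] = 2 × [1 − Φ(1.2)] = 23%.

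**Power after adjustment.** At 80% starting power the noncentrality is 1.645 + 0.842 = 2.486. If adjustment multiplies the variance of the estimate by R, power = Φ(2.486/√R − 1.645).

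*Absolute change, raw baseline as covariate, equal variances:* R = (1 + ρ)/2, with ρ the baseline to Day-14 correlation.

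| ρ | R | Power |
|---|---|---|
| 0.3 | 0.65 | 92.5% |
| 0.5 | 0.75 | 89.0% |
| 0.7 | 0.85 | 85.4% |

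The gain falls as ρ rises because the change score already uses baseline with a slope fixed at 1.

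*Percent decrease:* R = 1 − r², with r the correlation of percent decrease with the baseline covariate.

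| r | R | Power |
|---|---|---|
| 0 | 1.00 | 80% |
| 0.3 | 0.91 | 83.2% |
| 0.5 | 0.75 | 89.0% |

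**Checks.** For R = 0.75, noncentral t with 24 versus 48 subjects also gives 80.0% to 89.0%. Simulation of absolute change at ρ = 0.5 gives 80.6% to 89.0%. Simulation with percent change independent of baseline gives 80.5% unadjusted and 79.9% adjusted, which is no gain.

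**Sensitivity to starting power.** At correlation 0.5 the gain is 6.3 points from 30%, 10.0 from 50%, 10.8 from 60%, 5.9 from 90% and 3.4 from 95%.

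**Form of the covariate.** With lognormal SPD (assumed log-SD 1, raw correlation 0.5) and absolute change as outcome, raw baseline gives about 89% to 90%, but log baseline only about 83%. The covariate's scale has to match the outcome's.

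**Who has an SPD.** Protocol 9.2.5.1 counts disease as measurable without a nodal lesion: "In the absence of nodal disease, the presence of blasts in the cerebrospinal fluid", or more than 25% blasts in the marrow, is enough. For marrow-only subjects protocol 9.2.2 adds that "if no nodal disease is identified, subsequent imaging is not required". Such subjects belong to the Table 3 population but may have no SPD at baseline or at Day 14.

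**The case against.** The strongest reply is that nothing is invalid. A pre-specified t-test on change is unbiased under randomisation and controls type I error, and its standard error already allows for chance imbalance. Unadjusted comparisons are the plan's consistent choice: non-stratified log-rank and Cox, and chi-square. All of that stands. A reader might infer from the 23% imbalance figure that the planned comparison is biased; the documents do not support that.

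Second, a reader might infer a loss of nine power points. The step from 80% to 89% is correct arithmetic, but the documents support neither the 80% start nor the correlation of 0.5.

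Third, it is tempting to say that the gain holds on either scale. It does not. Percent decrease, which is the protocol's endpoint, already divides by baseline and may be uncorrelated with it; the covariate then gains nothing.

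Fourth, it is tempting to say that baseline SPD is available for everyone in the analysis set. It is available for everyone with a change value, but not for everyone in the Table 3 population.

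Finally, the stakes are low. Besides the testing order, protocol 9.1.3 and 9.2.5 call the Cycle 1 Day 14 imaging exploratory, and protocol 11.3.2 says only that the endpoint will be summarised. Protocol 11.9.1 reports the futility boundary reached at 31 events and enrolment stopped, so 48 versus 24 is unlikely to be attained. This lowers the importance of the point. It does not remove the possible gain in precision for the difference and 90% interval that SAP 5.5.4 still asks for.

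**Conclusion.** The point holds as an optional efficiency improvement. The planned Day-14 comparison omits a baseline covariate that is in hand for every subject with an SPD change.

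Conditional on an assumed 80% starting power at 2-sided 10%, adjustment would give about 85% to 92% for absolute change (ρ from 0.7 down to 0.3, equal variances). For percent decrease it would give from no gain at r = 0 to about 89% at r = 0.5. No single figure can be attached to this trial, because the documents give no power, SD or correlation for the endpoint and disagree on its scale. Practical impact is small.

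**What to change.** 1. Settle the outcome scale: SAP 5.5.4 says mean change, while SAP Table 3 and the protocol endpoint say percent decrease.
2. In SAP 5.5.4, Table 3 and 5.3.1, specify ANCOVA of that outcome on treatment with baseline SPD as covariate: log baseline SPD for percent or log-ratio change, raw baseline SPD for absolute change.
3. Restrict the analysis to subjects with a measurable SPD at baseline, and say so in Table 3.
4. Report the adjusted difference with its 90% confidence interval and keep the t-test as supportive.
5. Record the departure from protocol 11.3 in SAP section 9.

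The cost is SAP text and one degree of freedom (70 to 69 at 48 versus 24), with no new data. If percent decrease proves unrelated to baseline, that degree of freedom is the whole loss.
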